5. GENERAL ASPECTS FOR STATISTICAL ANALYSIS

5.1. General Methods

All analyses and summaries will be produced using SAS[®] version 9.4 (or higher). Data will be summarized descriptively by treatment group.

In general, continuous data will be summarized with descriptive statistics (number of patients, mean, standard deviation, median, minimum, and maximum) and will be analyzed using analysis of covariance (ANCOVA) techniques. Categorical variables will be summarized by sample size (N), frequency count, and percent, and will be analyzed using Cochran-Mantel-Haenszel (CMH) to evaluate the difference between treatments, controlling for disease duration category and baseline MGS score category. If CMH comparisons are not estimable, Pearson’s chi-square test or Fisher’s exact test (if the expected cell count is <5 in 25% or more of the cells) will be used.

For analysis purposes, assessments at **unscheduled** visits will be mapped to the nearest scheduled visit (e.g., analysis visit), using the following approach, as summarized in [Table 3](#). All unscheduled visits prior to the Baseline visit date, or in patients who have not had a Baseline visit, will be mapped to the Screening visit.

For assessments scheduled for every study visit: Study visits are scheduled to occur at 14, 42, 84, 126, and 168 days after the Baseline visit for the Day 14, Month 1.5, Month 3, Month 4.5, and Month 6 visits respectively. Therefore, the numbers of days between those visits, not counting the actual visit days, are 13, 27, 41, 41, and 41. Dividing those periods in half and rounding down, the windows around visits should extend to 6, 13, 20, 20, and 20 days after the scheduled visit day. The next window should start the day after the prior window ends, resulting in the following windows:

- Baseline visit date through Baseline visit date + 6: mapped to Baseline visit.
- Baseline visit date + 7 through Baseline visit date + 26: mapped to Day 14 visit.

- Baseline visit date + 27 through Baseline visit date + 61: mapped to Month 1.5 visit.
- Baseline visit date + 62 through Baseline visit date + 103: mapped to Month 3 visit.
- Baseline visit date + 104 through Baseline visit date + 145: mapped to Month 4.5 visit.
- Baseline visit date + 146 or later: mapped to Month 6 visit.

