For assessments not scheduled at every study visit: The same approach will be used, omitting the visits without planned assessments from the algorithm. For example, vital signs and Schirmer's assessment are planned for Baseline, Month 3, and Month 6 visits. The numbers of days between those visits are 83 in both cases, resulting in the first 41 days of the period being assigned to the earlier visit. Therefore:

- Baseline visit date through the Baseline visit date + 41 would be assigned to the Baseline visit;
- Baseline visit date + 42 through Baseline visit date + 125 would be assigned to the Month 3 visit, and
- Baseline visit date + 126 or later to the Month 3 visit.

In cases where an assessment is not scheduled to be performed at the Baseline visit, but is scheduled only at the Screening visit, Month 3, and Month 6, (such as IOP, meibography, or ophthalmology), visits prior to and including the Baseline visit will be windowed to the Screening visit, and visits between the Baseline and Month 3 visits will be windowed to Month 3. Visits between Month 3 and Month 6 will be split as described above.

Assessments conducted at the time of **early termination** (defined as assessments performed on the date of early termination or recorded on the same date as an End of Study visit is entered in the subject visit case report form [CRF] page) will also be mapped to the nearest planned visit, as described for unscheduled visits.

Table 3 Mapping of Unscheduled and Early Termination Visits

Visit	Date with Regards to Baseline Visit	Study Day	Analysis Visit Mapping		
			Assessments Performed Each Visit	Assessments Performed at Screening, Baseline, Month 3, and Month 6	Assessments Performed at Screening, Month 3, and Month 6
Screening	Baseline -14 d	-14	Screening	Screening	Screening
Baseline	Baseline	1	Baseline	Baseline	
			
	Baseline + 6 d	7			
	Baseline + 7 d	8			
			
Day 14	Baseline + 14 d	15	Day 14		Month 3

Visit	Date with Regards to Baseline Visit	Study Day	Analysis Visit Mapping		
			Assessments Performed Each Visit	Assessments Performed at Screening, Baseline, Month 3, and Month 6	Assessments Performed at Screening, Month 3, and Month 6
			
	Baseline + 26 d	27			
	Baseline + 27 d	28	Month 1.5		
			
	Baseline + 41 d	42			
Month 1.5	Baseline + 42 d	43			
	Month 3	Month 3	
	Baseline+61 d	62			
	Baseline+62 d	63			
			
Month 3	Baseline + 84 d	85	Month 4.5		
			
	Baseline+103 d	104			
	Baseline+104 d	105			
	Month 6	Month 6	Month 6
	Baseline+125 d	126			

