Month 4.5	Baseline+126 d	127			
			
	Baseline+145 d	146	Month 6		
	Baseline+146 d	147			
			
Month 6	Baseline + 168 d	169			
			
	End of Study				

Abbreviations: d = day(s).

Note: Ellipses indicate all dates between the prior and subsequent lines.

If multiple assessments are mapped to the same analysis visit (such as the scheduled visit and 1+ unscheduled visits), the following approach will be used:

- If only 1 non-missing result is present, that result will be used for summaries and analyses.
- If >1 non-missing result is present, the result collected later (chronologically) will be used for summaries and analyses.

All relevant patient data will be included in the listings. All information entered into the database will be included in patient data listings, including data not used for analysis purposes. Data will be listed by the nominal time point collected (whether a scheduled visit or unscheduled visit). Listings will display treatment as randomized. In the event that actual treatment differs from treatment as randomized, a footnote will be added to listings as appropriate, to provide specific information.

Summary statistics will be presented to the degree of precision provided in [Table 4](#).

Table 4 Reporting Precision

Statistics	Degree of Precision
Mean, Median, Quartiles, Confidence intervals	One more decimal place than the raw data
Standard deviation (SD), Standard error (SE)	Two more decimal places than the raw data
Minimum, Maximum	The same number of decimal places as the raw data
p-value	Rounded to 4 decimal places and formatted as 0.xxxx; values smaller than 0.0001 as '<0.0001'
Percent	One decimal place

All fractional numeric values will be presented with a zero to the left of the decimal point (for example, 0.12-0.30, not .12-.30).

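### SAP 5.1's mapping of unscheduled and early-termination values departs from its own rule twice: one window is labelled Month 3 instead of Month 6, and four window ends fall one day early

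*SAP*

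**What the plan says.** Days below are counted from the Baseline visit, so +62 means 62 days after it.

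SAP 5.1 maps values from unscheduled visits to the nearest scheduled visit and treats early-termination values the same way. The inputs for assessments done at every visit are explicit: "Study visits are scheduled to occur at 14, 42, 84, 126, and 168 days after the Baseline visit". The section counts the days in between, "the numbers of days between those visits, not counting the actual visit days, are 13, 27, 41, 41, and 41", halves them, rounds down, and concludes that "the windows around visits should extend to 6, 13, 20, 20, and 20 days after the scheduled visit day". It adds that "The next window should start the day after the prior window ends". The listed windows are 0 to +6, +7 to +26, +27 to +61, +62 to +103, +104 to +145, and +146 or later. The Month 3 line, for example, is "Baseline visit date + 62 through Baseline visit date + 103: mapped to Month 3 visit". Table 3 uses the same cut-offs.

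For assessments planned only at Baseline, Month 3 and Month 6 (vital signs and Schirmer's are the examples), the same method gives the first 41 days of each interval to the earlier visit. The text assigns 0 to +41 to Baseline and +42 to +125 to Month 3, and then says "Baseline visit date + 126 or later to the Month 3 visit". Table 3 carries a Month 6 label for the last block. IOP, ophthalmoscopy and meibography refer back to this split for the period between Month 3 and Month 6.

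When several values fall in one window, "the result collected later (chronologically) will be used for summaries and analyses".

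**The concern.** The first slip gives two adjoining windows the same label and leaves no window through which an unscheduled or early-termination value can reach Month 6. Such values will occur, because Protocol 1.2 (Visit Schedule) asks Expansion Cohort patients who stop early to complete the Month 6 procedures. With the later-value rule, a Schirmer's, vital-sign, IOP, ophthalmoscopy or meibography value at, say, +150 could take the place of the patient's scheduled Month 3 value.

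The second slip affects assessments done at every visit, which include MGYLS and OSDI. SAP 5.3.1.1 feeds mapped unscheduled and early-termination values into the primary multiple imputation. A patient who exits on +62 is therefore analysed with an observed Month 3 value. Under the stated rule that value belongs to Month 1.5, and Month 3 would be imputed. Conversely, an exit value on +104 in a patient with no Month 3 visit is placed at Month 4.5, although the rule puts it at Month 3.

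**Working it through.** **Every-visit assessments**

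Inputs (SAP 5.1): planned days 0, 14, 42, 84, 126 and 168.

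Days between visits = next day − this day − 1:
- 14 − 0 − 1 = 13
- 42 − 14 − 1 = 27
- 84 − 42 − 1 = 41
- 126 − 84 − 1 = 41
- 168 − 126 − 1 = 41

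Halved and rounded down: 6, 13, 20, 20, 20. Both sets match the SAP. The next step does not, apart from the Baseline window.

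Window end = visit day + extension:

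| Visit | Rule end | Listed end | Listed extension |
|---|---|---|---|
| Baseline | 0 + 6 = +6 | +6 | 6 |
| Day 14 | 14 + 13 = +27 | +26 | 12 |
| Month 1.5 | 42 + 20 = +62 | +61 | 19 |
| Month 3 | 84 + 20 = +104 | +103 | 19 |
| Month 4.5 | 126 + 20 = +146 | +145 | 19 |

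Exactly four days change visit, each time to the farther one:
- +27 goes to Month 1.5 (15 days away) instead of Day 14 (13 days).
- +62 goes to Month 3 (22 days) instead of Month 1.5 (20 days).
- +104 goes to Month 4.5 (22 days) instead of Month 3 (20 days).
- +146 goes to Month 6 (22 days) instead of Month 4.5 (20 days).

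One reading reproduces the listed ends. Treat 14, 42, 84 and 126 as Study Days with Baseline as Study Day 1, so that the ends are 14 + 13 − 1 = +26, 42 + 20 − 1 = +61, 84 + 20 − 1 = +103 and 126 + 20 − 1 = +145. The SAP rules this out: it counts the visits in days after Baseline, and Table 3 shows Baseline + 14 as Study Day 15.

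**Assessments not done at every visit**

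Planned days 0, 84 and 168. Days between: 84 − 0 − 1 = 83 and 168 − 84 − 1 = 83; half, rounded down, is 41. Ends: 0 + 41 = +41 and 84 + 41 = +125. Both cut-offs match the SAP. What remains, +126 onward, belongs to Month 6. Day +126 is 42 days from each visit and goes to the later one under the rule; from +127 (43 against 41 days) Month 6 is nearer. Only the label in the last bullet is wrong.

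**Size**

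The documents give no early-exit rate. Assume that a proportion p of 225 patients exits early, evenly over 168 days. The expected numbers are:
- on or after +126 (42 of the 168 days): 225 × p × 42/168
- on one of the four days: 225 × p × 4/168
- on +62 or +104: 225 × p × 2/168

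| p | On or after +126 | Four days | +62 or +104 |
|---|---|---|---|
| 5% (11.25 exits) | 2.8 | 0.27 | 0.13 |
| 10% (22.5 exits) | 5.6 | 0.54 | 0.27 |
| 20% (45 exits) | 11.25 | 1.07 | 0.54 |

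Unscheduled visits would add to these; their frequency is not given either.

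**The case against.** On the first slip, the defence is that the document already answers it. Table 3 is offered as the summary of the method and shows Month 6, the 41-day rule points the same way, and a cut-off between +125 and +126 would serve no purpose if both sides were Month 3. A careful programmer would probably read it correctly. That makes harm unlikely, but the SAP states no precedence between text and table, and the two still disagree.

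A reader might infer that values from +126 onward overwrite Month 3 results in the primary analysis. The documents do not support that. MGYLS and OSDI are done at every visit and follow the other list of windows. SAP 14 limits the Month 3 analysis to data through Month 3, apart from early-termination visits in patients with no Month 3 visit. The exposure lies mainly in the Month 6 supplemental outputs, where SAP 8 calls p-values for Month 4.5 and Month 6 data descriptive.

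On the second slip, the cut-offs are explicit, the same in text and table, and the same for every arm, so nothing is left to the programmer. That is fair: this is a departure from the stated rule and not an ambiguity. It would also be wrong to infer that four windows have become shorter. In total length only Day 14 loses a day (20 instead of 21). Month 1.5, Month 3 and Month 4.5 keep 35, 42 and 42 days and move one day earlier. Nor are scheduled visits re-assigned, because only unscheduled and early-termination values are windowed.

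Rewording the rule to match the listed windows would also remove the inconsistency, but the four days would still map to the farther visit, against the section's nearest-visit principle.

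**Conclusion.** Both inconsistencies are real and follow from the SAP's own figures; neither is large. The first is a wrong label that conflicts with Table 3. It concerns vital signs, Schirmer's, IOP, ophthalmoscopy and meibography only, and it does harm only if the bullet is programmed as written. In the 10% illustration about 5.6 patients would exit late enough to be exposed. The second is a one-day error in four window ends that can reach MGYLS and OSDI, with about 0.27 patient expected to exit on +62 or +104 in the same illustration. Even that overstates its effect on the primary analysis: an unscheduled +62 value gives way to a later scheduled Month 3 value, and a +104 exit matters there only if the Month 3 visit was missed. The counts rest on the assumed exit rate and even spread; the two contradictions do not. The comparison with Table 3 uses only its row breaks and visit labels, not the extent of its merged cells.

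**What to change.** Before the Month 3 database freeze:

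1. In SAP 5.1, change the visit named in the last bullet for assessments not done at every visit from Month 3 to Month 6, so that it agrees with Table 3.
2. Set the every-visit windows to 0 to +6, +7 to +27, +28 to +62, +63 to +104, +105 to +146, and +147 or later, and correct Table 3 to match.

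The cost is one label and a few programming constants. There is one minor downside. Under the later-value rule, an unscheduled value on +62 would replace the scheduled Month 1.5 value, and one on +104 would replace the scheduled Month 3 value (in the Month 6 outputs, given the data limit in SAP 14). The listed windows avoid this on those particular days, but it already happens for every other day in a window that follows the scheduled visit.

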10.9. Intraocular Pressure

IOP results will be categorized as <18, 18-25, or >25 mmHg separately in the study eye and non-study eye and summarized using a shift table. Results will be listed chronologically by patient and visit.

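### The latest-value rule in SAP 5.1 can drop transient between-visit safety findings from the by-visit and shift tables, and no worst post-baseline summary is planned to catch them

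*SAP*

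**What the plan says.** SAP 5.1 (General Methods) says that unscheduled "visits will be mapped to the nearest scheduled visit (e.g., analysis visit), using the following approach". Early-termination assessments are treated the same way.

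- **Assessments done at every visit** (among them BCVA, slit lamp and staining). "Study visits are scheduled to occur at 14, 42, 84, 126, and 168 days after the Baseline visit", and "the windows around visits should extend to 6, 13, 20, 20, and 20 days after the scheduled visit day". The first window is listed as "Baseline visit date through Baseline visit date + 6: mapped to Baseline visit". The later ones end at +26 (Day 14), +61 (Month 1.5), +103 (Month 3) and +145 (Month 4.5), and everything after that is Month 6.
- **Assessments done only at Screening, Month 3 and Month 6** (IOP, meibography and what is evidently ophthalmoscopy). Here "visits between the Baseline and Month 3 visits will be windowed to Month 3". After Month 3 the interval is split: SAP Table 3 assigns readings through +125 to Month 3 and later ones to Month 6.
- **More than one reading in an analysis visit.** "If >1 non-missing result is present, the result collected later (chronologically) will be used for summaries and analyses". The rule has no exception for safety data.

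On the output side, IOP is categorised "separately in the study eye and non-study eye and summarized using a shift table" (SAP 10.9). Ophthalmoscopy (10.8) and slit lamp (10.7) are also shift tables. BCVA (10.5) is summarised by time point, with 5- and 10-letter change categories. Neither these sections nor the table lists in SAP Appendices 4 and 5 include a worst post-baseline or any-occurrence summary.

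**The concern.** Unscheduled visits are where acute problems tend to be seen. A rule that keeps the last value in a window favours the recovered state over the abnormal one. Take a patient whose IOP is in the lowest category at Screening, above 25 mmHg at an unscheduled visit on day +30, and back in the lowest category at Month 3. The IOP shift table counts that patient as having no shift.

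If the investigator did not regard the finding as clinically significant, Protocol 8.3.1 does not make it an adverse event, and a line listing is then the only place it appears. Protocol 8.1.6 says that the Expansion Cohort has no data review committee, so no such committee is charged with reading those listings. Safety is part of the primary objective in SAP 2.1, and IOP, BCVA, biomicroscopy, ophthalmoscopy and hyperaemia are named safety endpoints in SAP 3.2. Protocol 2.3.2 also refers to reversible ocular findings with a 2.5% selenium disulfide shampoo. That is a different formulation and a higher strength than those tested here, but reversible findings are the kind a last-value rule can hide.

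**Working it through.** **Inputs.** Scheduled days 0, 14, 42, 84, 126 and 168, with the windows, come from SAP 5.1 and Table 3. The assessment schedule comes from SAP Table 2. Assumptions: scheduled visits fall on their nominal days with non-missing results, and there is one unscheduled reading per window.

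**The plan's own windows.** Days between visits, not counting visit days: 13, 27, 41, 41, 41. Halved and rounded down: 6, 13, 20, 20, 20. Window end = scheduled day + half:

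- 0 + 6 = +6 (stated +6)
- 14 + 13 = +27 (stated +26)
- 42 + 20 = +62 (stated +61)
- 84 + 20 = +104 (stated +103)
- 126 + 20 = +146 (stated +145)

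Four of the five stated ends are one day short of the SAP's own rule. The counts below use the stated windows; the rule's windows are checked at the end.

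**IOP and ophthalmoscopy, Baseline to Month 3.** Non-visit days +1 to +83 = 83. All map forward to Month 3, where the scheduled reading is later and is used. Replaced: 83 of 83 (100%).

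**IOP and ophthalmoscopy, to Month 6.** Non-visit days = 167 − 1 = 166. Replaced: 83 + 42 (+126 to +167) = 125 of 166 (75%). On the 41 days +85 to +125 the unscheduled reading is the later one and replaces the Month 3 value.

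**BCVA, slit lamp and staining, Baseline to Month 3.** Non-visit days = 83 − 2 = 81.

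| Days | Number | Mapped to | Result |
|---|---|---|---|
| +1 to +6 | 6 | Baseline | not in a post-baseline row |
| +7 to +13 | 7 | Day 14 | replaced by Day 14 |
| +15 to +26 | 12 | Day 14 | shown |
| +27 to +41 | 15 | Month 1.5 | replaced by Month 1.5 |
| +43 to +61 | 19 | Month 1.5 | shown |
| +62 to +83 | 22 | Month 3 | replaced by Month 3 |

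Replaced: 7 + 15 + 22 = 44 (54%). Shown: 12 + 19 = 31 (38%). Filed under Baseline: 6 (7%). Absent from post-baseline rows: 44 + 6 = 50 of 81 (62%).

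**BCVA, slit lamp and staining, to Month 6.** Non-visit days = 167 − 4 = 163. Replaced: 44 + 22 + 22 = 88 (54%). Shown: 31 + 19 + 19 = 69 (42%). Filed under Baseline: 6 (4%).

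**Sensitivity to the one-day discrepancy.** With the rule's windows, replaced days to Month 3 are 7 + 14 + 21 = 42 of 81 instead of 44. The conclusion does not change.

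**Days +1 to +6.** The first dose is planned for the evening of the Baseline visit (SAP 5.2.1), and SAP 5.2.2 takes baseline as the last measurement on or before the first-dose date. A reading on these days is therefore post-dose, yet it is filed under the Baseline visit.

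**The case against.** A reader might infer that every between-visit reading is pushed to the next planned visit, and so disappears from the safety tables altogether. The documents do not support that, for four reasons.

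- Forward mapping is the rule only for IOP, ophthalmoscopy and meibography before Month 3. BCVA, slit lamp and staining go to the nearest visit. In the days after each scheduled visit the unscheduled reading is the one that is shown, unless a further recheck falls in the same window.
- Safety tables include ophthalmic treatment-emergent adverse events overall, in the study eye and in the non-study eye (SAP 10.2). A clinically significant worsening belongs there under Protocol 8.3.1. A marked loss of vision or rise in IOP should be caught by that route.
- Every reading stays in the listings (SAP 5.1), and each of these assessments has its own (Listings 14, 15, 22, 24 and 25).
- Replacement requires a non-missing Month 3 result, not merely attendance. If the Month 3 IOP is missing, the unscheduled value is used.

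It can also be said that Protocol Table 3-1 asks only for shift tables, which the SAP supplies, that nothing in the documents promises a worst-value summary, and that no primary or multiplicity-controlled result is affected. All of this is correct. It narrows the point to findings that the investigator did not report as adverse events, and to by-visit and shift tables. It does not remove the gap: adverse event reporting depends on a judgement of clinical significance, whereas the tables of measured values are meant to show the measurements whatever that judgement was.

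**Conclusion.** The point holds in this limited form. Followed as written, the SAP can omit transient between-visit findings from the by-visit and shift tables. The omission is complete for IOP and ophthalmoscopy before Month 3 whenever the Month 3 result is present. For BCVA, slit lamp and staining it is partial: 50 of 81 non-visit days to Month 3.

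The counts rest on nominal visit days and a single unscheduled reading per window. They describe how much of the calendar the rule covers. The documents give no frequency for unscheduled readings, so the number of patients or events affected cannot be estimated. Efficacy conclusions are not at issue. This is a worthwhile and inexpensive improvement to safety reporting, not a flaw in the primary analysis.

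**What to change.** Keep the visit-mapped values for the by-visit rows. Add a worst post-baseline row, through Month 3 and through Month 6, using every scheduled, unscheduled and early-termination reading after the first dose, for:

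- IOP (SAP 10.9, Tables 36 and 36.1)
- ophthalmoscopy (SAP 10.8, Tables 35A/B and 35.1A/B)
- BCVA letter change (SAP 10.5, Tables 33 and 33.1)
- slit lamp including hyperaemia (SAP 10.7, Tables 15A–D and 15A.1–15D.1)
- optionally, staining. It is an exploratory efficacy endpoint, so its row belongs with SAP 8.3.1 and Tables 16 and 16.1, not in SAP section 10.

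Under the same assumptions, the days on which a lone unscheduled reading is left out of the post-baseline tables fall from 83 of 83 (IOP and ophthalmoscopy) and 50 of 81 (BCVA and slit lamp) to 0. Readings on days +1 to +6 would be included, because they follow the planned first dose.

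The cost is one SAP paragraph and a few rows in existing tables. The readings are already collected and listed, and no efficacy analysis or by-visit row changes. The safety tables may look slightly less favourable. In the same edit, reconcile the listed window ends with the half-gap rule.
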